### **9.3.2. Exclusion Criteria**

Eligible patients must not meet **any** of the following criteria.

1. Prior treatment with azacitidine (injectable or oral) or decitabine.
2. Treatment within 28 days prior to Cycle 1 Day 1 with:
  - Erythropoiesis stimulating agent (ESA),
  - Granulocyte colony-stimulating factor (G-CSF) and granulocyte-macrophage colony-stimulating factor (GM-CSF),
  - Lenalidomide.
3. Iron chelation therapy if initiated within 56 days prior to Cycle 1 Day 1.
4. Treatment with another investigational drug or device, or approved therapy for investigational use  $\leq 28$  days prior to Cycle 1 Day 1, or if the half-life of the previous product is known, within 5 times the half-life prior to Cycle 1 Day 1, whichever may be longer.
5. Major surgery within 28 days prior to Cycle 1 Day 1. Patients must have completely recovered from any previous surgery prior to Cycle 1 Day 1.
6. Platelet count  $< 30 \times 10^9/\text{L}$ .
7. Any active infection requiring parenteral antibiotic therapy within 28 days prior to Cycle 1 Day 1 or oral antibiotics within 14 days of Cycle 1 Day 1.
8. History of stroke, deep venous thrombosis (DVT) or arterial embolism within 6 months prior to Cycle 1 Day 1.
9. Known positive for human immunodeficiency virus (HIV), active infectious hepatitis B (HBV) or active infectious hepatitis C (HCV).

10. Any malignancy other than MDS which has not been in remission and/or has required systemic therapy including radiation, chemotherapy, hormonal therapy or surgery, within the last year prior to Cycle 1 Day 1.
11. Uncontrolled hypertension defined as systolic blood pressure (BP)  $\geq 150$  mm Hg or diastolic BP  $\geq 100$  mm Hg.
12. Pregnant or lactating females.
13. History of severe allergic or anaphylactic reactions or hypersensitivity to recombinant proteins or excipients in the investigational drug.
14. Any other condition not specifically noted above which, in the judgment of the investigator, would preclude the patient from participating in the study.
15. Transfusion event within 7 days prior to Cycle 1 Day 1.
16. Prior treatment with sotatercept (ACE-011), or ACE-536.
17. Secondary MDS.

#### **9.4. Patient Treatment Discontinuation and Withdrawal Criteria**

Patients will be informed that they have the right to discontinue treatment and/or withdraw from the study at any time for any reason without prejudice to their medical care.

A patient may be discontinued from treatment for any of the following reasons:

- Patient's request
- Patient's unwillingness or inability to comply with the protocol
- Pregnancy
- Use of prohibited medication (e.g., ESA)
- Medical reason or adverse event, at the discretion of the investigator and/or the medical monitor
- Lack of effect (e.g., worsening anemia for NTD patients as evidenced by sustained reduction in Hgb by  $\geq 2$  g/dL over 8 weeks or transfusion dependence), to be discussed with the medical monitor
- Disease progression (any of the following):
  - For patients with <5% blasts at baseline:  $\geq 50\%$  increase in blasts to > 5% blasts
  - For patients with 5-10% blasts at baseline:  $\geq 50\%$  increase in blasts to > 10% blasts  
(For patients with 5-10% blasts, a 2nd bone marrow sample may be collected within 4 weeks to confirm progression before discontinuing patients from treatment)
- Hypersensitivity reaction to study drug
- At the discretion of the sponsor (e.g., termination of the study or a dose level)

A patient may be withdrawn from the study for any of the following reasons:

- Patient's request
- Patient's unwillingness or inability to comply with the protocol
- Death
- Loss to follow-up
- At the discretion of the sponsor (e.g., termination of the study)

The reasons for study withdrawal and/or treatment discontinuation must be recorded in the patient's CRF. The investigator must notify the sponsor, the medical monitor and the contract research organization (CRO) immediately when a patient has been discontinued/withdrawn due to an AE. Patients who discontinue treatment early should complete the end of treatment (EOT) follow-up visit at the time of discontinuation and then complete the post-treatment follow-up (PTFU) and end of study (EOS) follow-up visits approximately 28 and 56 days later, respectively.

The investigator must notify the sponsor and the CRO when a patient has been discontinued/withdrawn for reasons unrelated to the study or study drug (e.g., withdrawn consent, lost to follow up).

## 10. TREATMENT OF PATIENTS

### 10.1. Selection and Timing of Dose for Each Patient

Once a patient is enrolled, the appropriate dose of ACE-536 will be administered as a subcutaneous injection on Cycle 1 Day 1. Subsequent doses will be administered every 3 weeks on Day 1 of the cycle. Study day  $85 \pm 2$  days is the last possible study day that ACE-536 can be administered, regardless of the cycle. Dose reductions may be required for individual patients as outlined in the Patient Dose Modifications Rules ([Section 10.8.1](#)). If a dose delay is required, the patient will return weekly for assessment of hematology results and adverse events until the patient is eligible to receive the next dose of ACE-536. Patients will be asked to return to the clinic for three follow up visits, occurring approximately 28, 56, and 84 days after their last dose of ACE 536. If a patient has a positive anti-drug antibody (ADA) result at the last visit, the patient may be asked to return for additional ADA testing every three months, until a negative result is obtained or the result is considered to be stabilized.

### 10.2. Concomitant Medications

During screening and throughout the study, patients may take stable doses of medications for chronic conditions that are not specifically excluded by the protocol (see [Section 9.3.1 Inclusion Criteria](#) and [Section 9.3.2 Exclusion Criteria](#)). If a patient requires treatment with any new medications that are specifically excluded by the eligibility criteria, the patient will be discontinued from the study and should complete the end of treatment visit and enter the follow-up period of the study. The investigator should consult the medical monitor regarding any questions about whether a new medication or dosage of existing medication would require the patient to discontinue from the study. Concomitant medications will be collected beginning at study screening and will include all medications taken within 28 days prior to Cycle 1 Day 1.

#### 10.2.1. Other Treatments for MDS

If treatment with azacitidine, decitabine, lenalidomide, ESA, or G-CSF is required during the ACE-536 treatment period, the patient should be discontinued from treatment with study drug and complete the end of treatment visit and enter the follow up period. Iron chelation therapy is allowed unless initiated within 56 days prior to C1D1.

#### 10.2.2. RBC Transfusions

For the first dose of ACE-536, dosing should occur after a minimum of 7 days post-transfusion and prior to any scheduled transfusions. Each TD patient will have a “pre-transfusion hemoglobin threshold” for requiring transfusion, which will be calculated based on transfusion history and will be used for determining when to transfuse during the study. The baseline pre-transfusion hemoglobin threshold will be the mean of all documented pre-transfusion hemoglobin values during the 12 weeks prior to C1D1. During treatment, if the pre-transfusion hemoglobin level is increased by  $\geq 1$  g/dL compared to the baseline pre-transfusion hemoglobin threshold for that patient, transfusion should be delayed by a minimum of 7 days and/or the number of units transfused should be reduced by 1 or more RBC units. Patients

should not be transfused if hemoglobin is  $\geq 9$  g/dL unless indicated for symptoms related to anemia or other reasons at the investigator's discretion.

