## 9.3. Selection of Study Population

### 9.3.1. Inclusion Criteria

Eligible patients must meet **all** of the following criteria:

1. Men or women  $\geq$  18 years of age.
2. Documented diagnosis of idiopathic/de novo MDS or non-proliferative chronic myelomonocytic leukemia (CMML) according to WHO criteria (white blood count [WBC]  $<$  13,000/ $\mu$ L) that meets IPSS classification ([Appendix 2](#)) of low or intermediate-1 risk disease as determined by the microscopic and standard cytogenetic analyses of the bone marrow and peripheral complete blood count (CBC) obtained during screening.
3. Anemia defined as:
  - Mean hemoglobin concentration  $<$  10.0 g/dL of 2 measurements (one performed within one day prior to Cycle 1 Day 1 and the other performed 7-28 days prior to Cycle 1 Day 1, not influenced by RBC transfusion within 7 days of measurement) for non-transfusion dependent patients (defined as having received  $<$  4 units of RBCs within 8 weeks prior to Cycle 1 Day 1) (Participation in all cohorts), OR
  - Transfusion dependent, defined as having received  $\geq$  4 units of RBCs within 8 weeks prior to Cycle 1 Day 1 (transfusion dependent patients are allowed in dose escalation cohorts and expansion cohort 1 only; patients with  $\leq$  6 units of RBCs within 8 weeks prior to Cycle 1 Day 1 may be allowed in cohort 2B).
4. Serum erythropoietin levels and prior erythropoiesis-stimulating agent (ESA) treatment:
  - Dose escalation cohorts and expansion cohort 1 patients: Serum erythropoietin level  $>$  500 U/L, OR, if  $\leq$  500 U/L, patient is non-responsive, refractory, or intolerant to erythropoiesis-stimulating agents (ESAs), or ESAs are contraindicated or unavailable.
  - Expansion cohort 2 patients: If patient is RS+ (defined as having  $\geq$  15% ring sideroblasts in the bone marrow), has less than 4 weeks' exposure to ESAs and serum erythropoietin level  $\leq$  200 U/L. If a patient is RS- (defined as having  $<$  15% ring sideroblasts in the bone marrow), prior ESA treatment and any serum erythropoietin level is allowed
5. No alternative treatment options, per national MDS guidelines, are available and/or appropriate for the patient, at the discretion of the investigator.
6. ECOG performance status of 0, 1, or 2 (if related to anemia).
7. Adequate renal (creatinine  $\leq$  2.0 x upper limit of normal [ULN]) and hepatic (total bilirubin  $<$  2 x ULN and AST and ALT  $<$  3 x ULN) function.

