5. STATISTICAL METHODOLOGY

5.1. Definitions

Low Transfusion Burden (LTB)

LTB patients are defined as those who received < 4 units of RBCs within 8 weeks prior to Cycle 1 Day 1.

High Transfusion Burden (HTB)

HTB patients are defined as those who required ≥ 4 units of RBCs within 8 weeks prior to Cycle 1 Day 1.

Baseline Hemoglobin

Baseline hemoglobin will be an average of hemoglobin measurements within 28 days of Cycle 1 Day 1, excluding measurements within 7 days following RBC transfusion.

Baseline Transfusion Burden

Baseline transfusion burden will be calculated as the total amount of RBC transfusion during the 8 weeks prior to Cycle 1 day 1.

Baseline for Other Parameters

Baseline erythropoietin (EPO) is defined as the maximum test value within 28 days of Cycle 1 Day 1. For all other parameters, baseline is defined as the last observation on or prior to Cycle 1 Day 1.

End of Treatment (EOT)

Procedures and evaluations for the end of treatment visit should be performed on Day 113 (± 7 days) (28 days after the last dose of ACE-536).

Post Treatment Follow-Up (PTFU)

Procedures and evaluations for the post treatment follow-up visit should be performed on Day 141 (± 7 days) (28 days after EOT visit).

End of Study (EOS)

Procedures and evaluations for the end of study visit should be performed on Day 169 (± 7 days) (56 days after the Day 113/EOT visit).

Patients who discontinue treatment early should complete the end of treatment visit at the time of discontinuation and complete the post-treatment follow-up (PTFU) and EOS follow-up visits 28 days (± 7 days) and 56 days (± 7 days) after the EOT visit.

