5.7.1. Primary Efficacy Endpoint

The primary efficacy endpoint is the modified erythroid response (mHI-E), defined as below:

- For low transfusion burden (LTB) patients, a hemoglobin increase of ≥ 1.5 g/dL from baseline for ≥ 14 days (in the absence of RBC transfusions). Hemoglobin measurements within 7 days following RBC transfusion will be excluded from analysis.
- For high transfusion burden (HTB) patients, a ≥ 4 units or $\geq 50\%$ reduction in RBC transfusion burden during any rolling 8-week window on treatment compared to baseline. The rolling 8-week window starts on Day 1 and increments by 1 day, e.g., from day 1 to day 56, day 2 to day 57, day 3 to day 58, etc.

A point estimate of the proportion of patients achieving a modified erythroid response will be presented along with its associated exact 95% confidence interval (CI) based on binomial distribution for LTB and HTB patients separately. The complete hemoglobin measurements and RBC transfusion records will be listed for each patient.

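### For HTB patients given units at hemoglobin 9 g/dL or above before entry, part of an mHI-E response can come from the on-study transfusion rule, and no planned response analysis separates it out

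*Protocol*

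**What the plan says.** **Before entry.** Protocol 9.3.1, criterion 3, gives "Transfusion dependent, defined as having received" at least 4 units in 8 weeks, with no limit on the hemoglobin at which they were given. SAP 5.1 does the same: "Baseline transfusion burden will be calculated as the total amount of RBC transfusion during the 8 weeks prior to Cycle 1 day 1".

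**On study.** Protocol 10.2.2 gives each TD patient an individual threshold, "which will be calculated based on transfusion history and will be used for determining when to transfuse during the study". That threshold "will be the mean of all documented pre-transfusion hemoglobin values during the 12 weeks prior to C1D1" and has no upper cap. The section then says patients "should not be transfused if hemoglobin is" 9 g/dL or above, "unless indicated for symptoms related to anemia or other reasons" at the investigator's discretion.

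**Endpoint.** For HTB patients, SAP 5.7.1 requires a fall of at least 4 units or at least 50%, as a "reduction in RBC transfusion burden during any rolling 8-week window on treatment compared to baseline". Protocol 15.2.2 makes the same comparison over 8 consecutive weeks. Neither sets a hemoglobin condition, and 15.2.2 rules out any comparison with controls.

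**HI-E.** Protocol 15.2.3, protocol Appendix 4 and SAP Appendix 3 tie the transfused-patient criterion to units given at hemoglobin 9.0 g/dL or below. The working definition in SAP 5.7.2.2 leaves that out.

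**The concern.** The baseline and on-study counts are collected under different rules. A unit given at 9 g/dL or above before entry raises the baseline. The same unit is discouraged on study, so it tends to be missing from the count it is compared with. The difference always favors response. With a single arm, a change of practice at entry cannot be told apart from a treatment effect, and the affected quantity is the primary endpoint in HTB patients. HI-E as defined in SAP 5.7.2.2 offers no check, because it has lost the qualifier that would have limited the problem.

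The two sentences in 10.2.2 also pull apart for a TD patient whose mean pre-transfusion hemoglobin is 9 g/dL or above. The individual threshold points to transfusion at a level where the general sentence advises against it.

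**Working it through.** The plan gives no figure on this point: neither the share of pre-study units given at 9 g/dL or above nor the response expected from changed practice. There is nothing to reproduce, so the check is what the definitions allow.

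**1. Units needed.** With B baseline units, the smallest qualifying fall is min(4, B/2 rounded up):

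| B | Units | Share of B |
|---|---|---|
| 4 | 2 | 50% |
| 6 | 3 | 50% |
| 8 | 4 | 50% |
| 10 | 4 | 40% |
| 12 | 4 | 33% |

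Cohort 2B admits at most 6 units, so a patient there with 4 to 6 baseline units needs a fall of 2 or 3.

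**2. Same patient, two ways of counting, no drug effect.**
- Baseline 4 units, 2 of them at 9 g/dL or above; on study only the other 2 are given. As written: 4 to 2, (4 − 2)/4 = 50%, a responder. Counting only units below 9 g/dL in both periods: 2 to 2, a 0% fall.
- Baseline 8 units, 4 of them at 9 g/dL or above; on study only the other 4 are given. As written: 8 − 4 = 4 units, a responder. Like for like: 4 to 4, no response.

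**3. Weight of one patient.** Expansion cohort 1 is to include at least 10 TD patients, if feasible. At exactly 10, one such patient moves the HTB rate by 1/10 = 10 percentage points.

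**4. Illustrative size.** A simulation with no drug effect used assumptions that are not in the documents: 2-unit transfusions, +1 g/dL per unit, a fall of 0.4 to 1.0 g/dL per week, weekly checks, measurement SD 0.3, and 1,500 patients with at least 4 baseline units per setting. The rule was modeled as lowering the trigger to 9.0 g/dL from Day 1, with the discretionary exception never used. Day 141 is Day 85 (last dose) + 56, the cut-off in SAP 5.7.

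| Historical trigger (g/dL) | Days 1–56, without → with rule | Any rolling window to Day 141, without → with rule |
|---|---|---|
| 8.5 | 2.6% → 3.0% | 18.6% → 19.7% |
| 9.0 | 2.1% → 2.9% | 19.3% → 18.2% |
| 9.5 | 2.5% → 8.9% | 16.9% → 20.0% |
| 10.0 | 2.7% → 16.8% | 18.3% → 24.7% |

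In the first two rows the trigger is unchanged by construction, so the differences are noise. The standard error of an 18.3% rate is √(0.183 × 0.817/1500) ≈ 1.0 point. In the last two rows the rule adds about 3 and 6 points under the rolling window. The rolling window itself produces most of the no-effect responses, about 17% to 19%.

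**5. Does anything planned remove it?** SAP 5.7.2.9 summarizes change in pre-transfusion hemoglobin in HTB patients, and SAP 5.6.2 lists transfusions with the preceding hemoglobin. Both help interpretation; neither changes who counts as a responder.

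**The case against.** The best defense is that 10.2.2 already ties on-study practice to the patient's own history. The 9 g/dL sentence matters only for units given at that level before entry, and it is discretionary. Withholding is also partly delay: a transfusion put off may still fall within the window. All of this stands, and it limits both the reach and the size.

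A reader might infer more in four ways.
- **That the HTB response rate is largely an artefact of the rule.** The documents do not support this. They give no distribution of pre-transfusion hemoglobin, and the rule has no effect on patients historically transfused below 9 g/dL.
- **That the delay-or-reduce instruction in 10.2.2 is part of the same problem.** That instruction, "transfusion should be delayed by a minimum of 7 days and/or the number of units transfused should be reduced by 1 or more RBC units", applies when hemoglobin is at least 1 g/dL above the patient's own threshold. This is a within-patient rise, which an active drug should produce, and it is not counted here.
- **That the two transfusion sentences flatly contradict each other.** The exception for symptoms or discretion leaves room to follow either. It is an unresolved tension for thresholds of 9 g/dL or above.
- **That a false-positive rate is inflated.** SAP 5.2 and 5.7 plan no formal testing, so no decision rule is affected; the effect is on a reported rate.

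One caveat on versions: the SAP follows protocol amendment 06 and includes an expansion cohort 3 that the supplied protocol lacks. The wording of 10.2.2 in that amendment cannot be confirmed. The supplied protocol raises the same point through its own 15.2.2.

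**Conclusion.** The point holds for a limited group: HTB patients with units given at 9 g/dL or above before entry. For them, baseline and on-study counts are not like for like, the difference favors response, and the planned analyses describe it without removing it. What matters is the individual units: a patient whose mean pre-transfusion value is below 9 g/dL may still have some baseline units above it.

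The size cannot be derived from the documents. The arithmetic shows that 2 to 4 units suffice; the simulation suggests a few percentage points under the rolling window, conditional on its assumptions and on historical triggers of 9.5 to 10.0 g/dL. This is a modest, correctable weakness in interpreting the HTB rate and does not invalidate the endpoint.

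**What to change.** 1. **Protocol 10.2.2.** The sponsor should reconcile the individual threshold with the 9 g/dL sentence for TD patients whose mean pre-transfusion hemoglobin is 9 g/dL or above. Which should govern is a clinical decision and is not proposed here.
2. **SAP 5.7.1.** Add one supplementary HTB mHI-E table that counts only units with pre-transfusion hemoglobin below 9.0 g/dL, in both the 8-week baseline and the on-treatment windows, among patients with at least 4 such baseline units. Treat units with no recorded value identically in both periods and show two versions: all counted, then all excluded. Report the number missing per period. Excluding them at baseline but counting them on study would bias the rate downward.
3. **SAP 5.7.2.2.** Restore the 9.0 g/dL-or-below qualifier for HI-E in transfused patients. It differs from the table in item 2 only at exactly 9.0 g/dL; the table's limit mirrors the on-study rule, and the HI-E limit follows the IWG criterion.
4. **Reporting.** Show the supplementary rate beside the main rate, and note that the main rate may include an effect of the on-study transfusion rule.

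**Cost.** SAP wording and one extra table. No new data collection is needed: protocol 12.2 collects the value before each on-study transfusion, 10.2.2 relies on documented values for the preceding 12 weeks, and SAP 5.6.2 already lists them. The downside is a smaller set, wider intervals and possibly a lower rate.

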### **10.3. Treatment Compliance**

ACE-536 will be administered as a SC injection at the clinical site by the study staff and will be documented in the study record. Monitoring for patient compliance with the treatment regimen is therefore unnecessary.

### **10.4. Randomization**

This is an open-label study and a randomization scheme is not needed for this study.

### **10.5. Treatments Administered**

Patients will continue to receive the same dose level of study drug as they were assigned at study entry unless a dose modification is required (see [Section 10.8](#), Patient Dose Modification Rules).

### **10.6. Dose-Limiting Toxicity Definition**

A Dose-Limiting Toxicity (DLT), using the current active minor version of the National Cancer Institute Common Toxicity Criteria for Adverse Events version 4.0 (NCI-CTCAE v4.0), is defined as any of the following toxicities, at any dose level occurring within 28 days of the first administered dose:

- Treatment-related serious adverse event (SAE) of Grade  $\geq 3$
- Treatment-related non-hematologic and non-infectious adverse event (AE) of Grade  $\geq 3$
- Treatment-related hematologic or infectious AE of Grade  $\geq 4$

### **10.7. Safety Evaluation and Dose Escalation**

Safety will be evaluated by the Safety Review Team (SRT), which is comprised at minimum of the coordinating investigator, medical monitor, and an independent hematologist. The role of the SRT will be described in greater detail in the SRT Charter. The SRT will review safety data when a minimum of 3 patients in a cohort have completed Study Day 29, including dose-limiting toxicities (DLTs), adverse events (AEs), serious adverse events (SAEs), laboratory results (including hematology and chemistry), vital signs, and erythroid response data. The SRT may make one or more of the following recommendations to the sponsor:

- Enroll 3 additional patients in the current cohort.
- Enroll 3 patients in a new cohort at a higher or lower dose level, not to exceed modified Fibonacci dose escalation scheme (see [Section 9.1](#)).
- Proceed to expansion cohort 1, with a recommended starting dose level not to exceed the maximum dose level evaluated in the dose escalation cohorts.
- Postpone a decision pending collection of additional data from the current cohort.

SRT recommendations to escalate or reduce the dose level of ACE-536 in a subsequent cohort or to continue dosing in the current cohort will be based in part upon the following criteria:

- If a DLT occurs in 0 out of a minimum of 3 patients in a cohort within 28 days following the initial dose, dose escalation may occur.
- If a DLT occurs in 1 out of 3 patients in a cohort within 28 days following the initial dose, an additional 3 patients should be enrolled in the current cohort.
  - If a DLT occurs in 1 out of 6 patients in a cohort within 28 days following the initial dose, dose escalation may occur.
- If a DLT occurs in  $\geq 2$  patients in a cohort within 28 days of the initial dose, the dose level for the next cohort (if any) should not be escalated; a lower dose level may be recommended.
- If a hemoglobin increase of  $\geq 2.0$  g/dL occurs in  $\geq 2$  patients in a cohort within 28 days of the initial dose, the dose level for the next cohort (if any) should not be escalated; a lower dose level may be recommended.

In addition, during enrollment of the expansion cohorts, the SRT will review safety data periodically throughout the trial, including AEs, SAEs, laboratory results (including hematology and chemistry), vital signs, and erythroid response data.

